7.10. Investigational Product Preparation, Handling, Storage, and Accountability

All IP preparation, handling, storage, and accountability will be the same as in the Main Study as in Section 6.

7.11. Dose Adjustment Criteria

Dose adjustment criteria are the same as the Main Study and can be found in Section 6.

7.12. Criteria for Investigational Product/Study Termination

All criteria for IP and study termination are the same as in the Main Study and can be found in Section 8.

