Study Week ¹ (following Week 24 in Main Study)	D1 Clinic	Wk 2 (D14) Telemed/	Wk 4(D28) Clinic	Wk 8 (D56) Clinic or	Wk 12 (D84) Clinic	Wk 18 (D126)	Wk 24 (D168)	ET ² Clinic or Home
	(Week 24	Phone Call		Home		Clinic or	Clinic	
	Main Study)					Home		
Efficacy-Related Assessments								
LMM9			X		X		X	
Right Heart Catheterization (RHC) ⁸							X	X
Echocardiography ⁹					X		X	
WHO FC			X		X		X	
Plasma NT-proBNP level			X		X		X	
PAH Symptoms and Impact Questionnaire (PAH-SYMPACT)					X		X	
Selexipag PK Sampling ¹⁰	X		X					
	a series a series a							

Visits at Week 2 (Telemed/Phone Call) and Week 4 (clinic visit) can occur within +/-2 days from the randomization date; Visits at Weeks 8 (Telemed/Phone call), 12 (clinic),

18 (clinic or home visit), 24 and 28/Follow Up (clinic) can occur within +/-5 days from the randomization date.

Patients who withdraw consent should be asked to complete the ET Visit for safety. Patients who withdraw consent will continue to be followed for vital status from public records such as government vital statistics or obituaries, as allowed by local law, or periodic contact (about every 6 to 12months).

Weight only (no height or BMI) will be performed at Weeks 4, 8, 12, 24, and 28.

⁴ IP must be taken daily, morning and evening. Doses should be taken with food. During visits at the clinic or home, all assessments should be done predose, except where otherwise indicated. Patients should bring their IP with them for each visit (including any empty bottles).

Pregnancy tests not required for women who are surgically sterile. Pregnancy tests will be completed in women of child-bearing potential every 4 weeks while on study. Weeks 8, 16 and 20 will be performed at home (with a kit given to the subject by the site) and the results will be confirmed with the subject by a phone call. Additional pregnancy tests should be completed anytime menstruation is delayed and in women with infrequent or irregular menstrual cycles.

Single 12-lead ECGs will be collected at all time points.

⁷Coagulation testing will be done at Weeks 12 and 24.

8 Week 24 RHC may occur up to 7 days prior to or on the Week 24 Visit. If a patient terminates early, and at or after the Week 12 Visit, an RHC should be performed at the Early Termination Visit.

⁹ Echocardiography should be done in supine position after at least 5 minutes of rest.

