10 Selexipag and ACT-333679 PK (for subjects using selexipag at baseline only): At Day 1 and Week 4, a predose PK sample will be collected (patients will take selexipag in the clinic at these visits, and the PK samples will be collected approximately 12 h after the prior dose) Additional unscheduled safety assessments may be conducted at any time during the study if the Investigator or Sponsor deems it necessary for the safety of the

Clinical Study Protocol Altavant Sciences GmbH

HADS = Hospital Anxiety and Depression Scale; HR = heart rate; IP = investigational product; IRT = interactive response technology; LFTs = liver function tests; mo = months; NT-proBNP = N-terminal pro-brain natriuretic peptide; OLE = Open-Label Extension; PAH = pulmonary arterial hypertension; PAH-SYMPACT = Pulmonary Arterial Hypertension Symptoms and Impact Questionnaire; QIDS-C = Quick Inventory of Depressive System-Clinician Rated; RHC = right heart catheterization; RR = respiratory rate; Abbreviations: 5-HIAA = 5-hydroxyindoleacetic acid; 6MWT = 6-minute walk test; AEs = adverse events; BMI = body mass index; BP = blood pressure; C-SSRS = Columbia-Suicide Severity Rating Scale; D = day; ECG = electrocardiogram; ET = early termination; FSH = follicle stimulating hormone; FU = follow up; SAE = serious adverse event; temp = temperature; WHO FC = World Health Organization Functional Class; Wk = week

Schedule of Assessments – Open-Label Extension – (Post 24 Weeks of the Open-Label Extension) 1.5.

	Pregnancy Test	Clinic Visits ⁴	Follow Up ⁴
			(T weeks after last uest of
Week	Every 4 Weeks (+/- 2 days)	Every 24 Weeks (+/- 4 days)	
IP Dispensing via IRT ¹		X	
IP Compliance/ Accountability ²		X	
Concomitant medications	X	X	
Vital Signs (BP, HR, RR, temp, oxygen saturation)		X	X
Pregnancy Test (serum/urine) ³	X	X	X
Laboratory - Hematology, Coagulation, Chemistry (including LFTs)		X	X
Adverse Events	X	X	X

¹ As necessary, 6-month supply of IP will be dispensed.

Additional unscheduled safety assessments may be conducted at any time during the study if the Investigator or Sponsor deems it necessary for the safety of the

² Patients should be instructed to bring their used, partial, and unused IP containers with them to every Clinic Visit to assess compliance and IP accountability.

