³ Pregnancy test will be required every 4 weeks, in women of childbearing potential only. Urine pregnancy kits will be provided to the patient. Completion of the pregnancy test, and collection of adverse events and concomitant medications will be documented via telephone contact. Serum pregnancy test to be done to confirm a positive urine test. Additional pregnancy tests should be completed anytime menstruation is delayed and in women with infrequent or irregular menstrual cycles.

⁴ If a patient discontinues IP for any reason a follow-up visit must be performed 4 weeks after the last dose of ID.

Abbreviations: BP = blood pressure; HR = heart rate; IP = investigational product; RT = interactive response technology; LFTs = liver function tests; RR = respiratory rate; temp = temperature

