	Impact on Eligibility	Monitoring and Stopping Criteria OR Management Criteria
Hepatic enzyme elevations	Exclude patients with alanine aminotransferase (ALT) / aspartate aminotransferase (AST) / gamma-glutamyl transferase (GGT) results greater than 2X upper limit of normal (ULN) and/or TBL > 2X ULN	Withdrawal criteria for abnormal liver function tests set at: • ALT or AST > 3X ULN and TBL > 2X ULN (or international normalized ratio (INR) > 1.5) • ALT or AST > 3X ULN with appearance of fatigue, nausea, vomiting, right upper quadrant pain or tenderness, fever, rash and/or eosinophilia (> 5%) • ALT or AST > 5X ULN for > 2 weeks • ALT or AST > 8X ULN
Cardiac arrhythmia, related to an increase in QT/QTc interval	 Exclude patients with: QTcF > 450 ms (males) or > 470 ms (females) Known congenital Long QT Syndrome (LQTS), or known family history of LQTS Clinically significant electrolyte abnormality (i.e., hypokalemia, hypocalcemia, hypomagnesemia) Concomitant use of QT-prolonging drugs clearly associated with a risk of Torsades de Pointe (see Appendix 1) 	Withdrawal criteria for abnormal/worsening QT interval prolongation: • QTcF interval > 500 ms • QTcF interval > 480 ms AND increase from baseline ≥ 60 ms • QTcF interval > 480 ms associated with syncope, life-threatening arrhythmias, resuscitated cardiac arrest, or seizure

ciences GmbH Effective: 19JAN2022

Protocol RVT-1201-2002

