7.4. Open-Label Extension Design

Patients in the Main Study that do not discontinue prematurely and complete up to and including the Week 24 Visit, have the option to rollover into the OLE. Patients who continue into the OLE will be blinded to the treatment they received in the Main Study. Patients who received active IP in the Main Study will remain on their regimen. Patients randomized to placebo in the Main Study will be re-randomized to one of the 2 active rodatristat ethyl treatment arms (300 mg BID or 600 mg BID) in the OLE.

Patients who participate in the OLE will continue to receive rodatristat ethyl for 6.5 years, until the Investigator or patient chooses to stop the IP, any stopping criteria in the Main Study are met, IP becomes commercially available, or the Sponsor stops the study for lack of efficacy or a safety signal (whichever preceding criteria comes first). In no case will a patient be allowed to exceed 10 years of exposure unless the product is approved for a chronic indication.

During the OLE patients will be followed by the Investigator according to clinical practice, with formal (per protocol) safety assessments. These safety assessments will include AEs, clinical laboratory tests, vital signs, and concomitant medications. Female patients of childbearing potential will be required to use 2 reliable methods of contraception to reduce the risk of pregnancy during the course of the study and for at least 30 days following the last dose of rodatristat ethyl.

During the first 24 weeks of the OLE patients, will also undergo efficacy assessments. These efficacy assessments will include 6MWT, RHC, echocardiogram, WHO FC, and plasma NT-proBNP level. Urine pregnancy tests will be performed every 4 weeks in women of child-bearing potential only, while the patient is on IP and once at 4 weeks post dose. If there is not a clinic visit, a urine pregnancy test will be sent home with the patient and results will be followed up with a phone call. Additional pregnancy testing in women whose menstruation is delayed or who have infrequent or irregular menstrual cycles should be conducted as warranted.

See SoA in Section 1.4 and Section 1.5.

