8.1. Discontinuation of Investigational Product

The Medical Monitor should be notified of any change to background PAH therapy to determine any need for withdrawal. See Section 8.2 for study withdrawal procedures.

Patients meeting any of the following liver chemistry criteria must be withdrawn (IP should be discontinued immediately) from the study by the Investigator:

- ALT or AST > 3X ULN and TBL > 1.5X ULN or INR > 1.5
- ALT or AST > 3X ULN with the appearance of fatigue, nausea, vomiting, right upper quadrant pain or tenderness, fever, rash, and/or eosinophilia (> 5%)
- ALT or AST > 5X ULN for more than 2 weeks
- ALT or AST >8X ULN

If liver chemistry tests meet any of the above criteria, repeat testing should be performed within 48 to 72 hours and the patient followed until resolution.

Patients meeting any of the following confirmed QT/QTc-related criteria must be withdrawn from the study by the Investigator:

- QTcF interval > 500 ms
- QTcF interval > 480 ms AND increase from Baseline ≥ 60 ms
- QTcF interval > 480 ms associated with syncope, life-threatening arrhythmias, resuscitated cardiac arrest, or seizure

The Investigator must also discontinue/withdraw a patient's participation in the study if any of the following criteria apply:

- Pregnancy
- Significant protocol violation/lack of compliance with the study and/or study procedures non-compliance with IP for discontinuation of patient is defined as < 50%.
- Severe constipation (e.g., obstipation with manual evacuation indicated) and/or severe, persistent, or worsening abdominal pain
- Any significant worsening on postdose C-SSRS indicative of active suicidal ideation with intent to act (defined as C-SSRS Suicidal Ideation category score of 4 or 5) or behavior (either preparatory acts/behavior, aborted attempt, interrupted attempt, or actual attempt)
- Severe depression or anxiety based on a HADS Depression or Anxiety score ≥ 15, or a QIDS-C Total Score ≥ 16.

• Any severe psychiatric or CNS AE as determined by the Investigator.

The Investigator may discontinue/withdraw a study patient's participation in the study if any of the following criteria apply:

Protocol RVT-1201-2002

Effective: 19JAN2022

• Behavioral or administrative reason

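### After OLE Week 24 the mandatory QTcF withdrawal rules still apply, but no ECG is scheduled for up to about 6 years on drug

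*Protocol*

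**What the plan says.** Two sections carry the Main Study stopping rules into the OLE. Section 7.4 continues treatment for 6.5 years unless one of several events comes first, among them that "any stopping criteria in the Main Study are met". Section 7.12 adds: "All criteria for IP and study termination are the same as in the Main Study and can be found in Section 8".

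Section 8.1 leaves no discretion over the QT rules: "Patients meeting any of the following confirmed QT/QTc-related criteria must be withdrawn from the study by the Investigator". The three criteria are:

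- QTcF above 500 ms;
- QTcF above 480 ms together with a rise from baseline of at least 60 ms;
- QTcF above 480 ms with syncope, life-threatening arrhythmia, resuscitated cardiac arrest or seizure.

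The risk table in Section 2.3 lists the same thresholds under "Withdrawal criteria for abnormal/worsening QT interval prolongation". They are the stated monitoring and stopping measure for QT-related arrhythmia. The text above that table defers the QT question to a future thorough QT study and treats such arrhythmia as a potential event of special interest until more is known.

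For the first 24 OLE weeks, the ECG footnote in Section 1.4 reads: "Single 12-lead ECGs will be collected at all time points". After that, Section 1.5 sets a clinic visit every 24 weeks. Its rows are IP dispensing, compliance, concomitant medications, vital signs, pregnancy test, adverse events and "Laboratory - Hematology, Coagulation, Chemistry (including LFTs)". Section 7.4 describes the formal OLE safety assessments in the same way: "These safety assessments will include AEs, clinical laboratory tests, vital signs, and concomitant medications".

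**The concern.** A mandatory withdrawal rule needs a measurement that can show when it is met. After OLE Week 24 the liver and pregnancy rules keep theirs, because liver tests and pregnancy tests stay in Section 1.5. The QTcF rules do not.

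The first two QTcF rules matter most here. They are defined by the tracing alone, and a patient who feels well gives the investigator no prompt to order one. A site could follow the plan exactly and never learn that a patient on 300 or 600 mg BID had crossed 500 ms.

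The consequence is for long-term safety. The OLE's stated objective includes long-term safety, yet after its Week 24 it would produce no systematic QTcF data while the protocol regards the question as open. The primary comparison in the Main Study is not touched.

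**Working it through.** The plan gives no figure for this gap, so there is none to reproduce. The check is a comparison of the schedules, followed by date arithmetic.

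**1. Is the ECG really absent?** Three places agree. The table in Section 1.5 has no ECG row. Its abbreviation list has no entry for ECG, whereas the lists under Sections 1.3 and 1.4 do. The Section 7.4 list does not name ECG. A fault in the text extraction is therefore unlikely.

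Section 9.2.4 describes how ECGs are recorded but sets no further visits, and Section 9.2.1 refers to Sections 1.3 to 1.5 for the timing of all safety assessments.

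**2. ECG coverage by phase (nominal visits on treatment)**

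| Phase | Scheduled ECG visits | Longest gap between them |
|---|---|---|
| Main Study | Weeks 4, 8, 12, 18, 24 (5) | Day 84 to 126, and 126 to 168: 42 days |
| OLE, first 24 weeks | Weeks 4, 8, 12, 18, 24 (5), plus early termination | 42 days |
| OLE after Week 24 | none | remainder of treatment |

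**3. Length of the last phase.** Inputs: 6.5 years of OLE treatment (Section 7.4), 24 weeks = 168 days already covered (Section 1.4), and one clinic visit per 168 days (Section 1.5).

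- OLE length: 6.5 × 365.25 = 2374.1 days
- Less the first 24 weeks: 2374.1 − 168 = 2206.1 days
- In years: 2206.1 / 365.25 = 6.04
- In clinic visits: 2206.1 / 168 = 13.1
- Share of the OLE: 2206.1 / 2374.1 = 93%

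**4. Other reading of the 6.5 years.** If they were counted from Main Study Day 1, a further 168 days come off: (2374.1 − 336) / 365.25 = 5.58 years, or 2038.1 / 168 = 12.1 visits. The description of up to about 6 years holds on either reading.

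**5. Which rules are left without a scheduled measurement?** All three need an ECG. The third also needs a clinical event, which would normally lead to an ECG being taken. The first two have no such trigger.

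**The case against.** The strongest reply is that the rules can still work. Section 8.1 does not require the qualifying ECG to be a scheduled one. Section 1.5 permits unscheduled safety assessments at any time if the investigator or sponsor thinks them necessary, Section 7.4 has patients followed under clinical practice, and Section 7.8 tells patients to call or return promptly after an adverse event. A reader might infer from the missing row that the QTcF rules cannot operate at all. The documents do not support that: the symptom-linked third rule can work through exactly these routes. What remains is that nothing prompts an ECG in a patient without symptoms.

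The second reply is that the lighter schedule is a deliberate step-down. By OLE Week 24 every continuing patient has had five scheduled ECG visits on active drug, and those on active drug from the start have had ten. Trough levels reach steady state by Day 5 (Section 2.1). Section 1.5 also drops the C-SSRS, HADS and QIDS-C, which serve other mandatory rules, so QT was not singled out. This is fair, and it lowers the weight of the point. But the protocol gives no reason for stopping ECGs while it calls the QT question open. Section 7.9 also allows a patient's dose to be changed to 600 mg BID depending on the timing and outcome of the 24-week analysis. If that happens after OLE Week 24, no ECG is planned at the new dose. The sponsor's own rationale for Amendment 3, which added ECGs and other safety checks at Week 8, was to avoid eight weeks between visits.

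A reader might also infer that the general permission for anti-emetics (Sections 1.1 and 4.4.1) opens the door to QT-prolonging ones. It does not: Section 6.6.3 and Appendix 1 prohibit the listed drugs, including ondansetron, domperidone and droperidol, so their use would be a deviation.

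Nor do the documents establish that only women of childbearing potential are telephoned every 4 weeks. The footnote in Section 1.5 limits the pregnancy test to them, but its next provision, "Completion of the pregnancy test, and collection of adverse events and concomitant medications will be documented via telephone contact", does not expressly limit the collection of events and medications. Both matters are optional clarifications and carry no weight here.

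**Conclusion.** The point holds as a gap in planned monitoring. For up to about 6.0 years of OLE treatment (5.6 on the shorter reading) and about 13 clinic visits, two mandatory QTcF withdrawal rules that need no symptoms have no scheduled measurement behind them.

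The 6.0 years is a maximum for a patient who stays for the full OLE. The documents give no rollover or retention rate, no QT event rate and no expected date for the thorough QT study. Total patient-time without an ECG, and the number of cases that might be missed, therefore cannot be estimated from them. The evidence behind the QT concern sits in the Investigator's Brochure, which is not among the documents, and the protocol calls the risk potential.

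This is an inexpensive improvement worth considering. It is not a flaw in the Main Study.

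**What to change.** In Section 1.5, add a single 12-lead ECG row to the 24-weekly clinic visit and to the follow-up visit. In Section 7.4, name ECG among the formal OLE safety assessments. Keep both at least until the thorough QT study reports. If the sponsor prefers to stop ECGs at OLE Week 24, the protocol should say why.

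The cost is about 13 brief, non-invasive ECGs per patient over a full OLE, plus one at follow-up, all at visits already planned. The Main Study schedule and analysis do not change.

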8. DISCONTINUATION OF INVESTIGATIONAL PRODUCT AND PATIENT DISCONTINUATION/WITHDRAWAL

Unnecessary withdrawal of patients should be avoided, and all efforts should be made to retain patients in the study.

8.1. Discontinuation of Investigational Product

The Medical Monitor should be notified of any change to background PAH therapy to determine any need for withdrawal. See Section 8.2 for study withdrawal procedures.

Patients meeting any of the following liver chemistry criteria must be withdrawn (IP should be discontinued immediately) from the study by the Investigator:

- ALT or AST > 3X ULN and TBL > 1.5X ULN or INR > 1.5
- ALT or AST > 3X ULN with the appearance of fatigue, nausea, vomiting, right upper quadrant pain or tenderness, fever, rash, and/or eosinophilia (> 5%)
- ALT or AST > 5X ULN for more than 2 weeks
- ALT or AST >8X ULN

If liver chemistry tests meet any of the above criteria, repeat testing should be performed within 48 to 72 hours and the patient followed until resolution.

Patients meeting any of the following confirmed QT/QTc-related criteria must be withdrawn from the study by the Investigator:

- QTcF interval > 500 ms
- QTcF interval > 480 ms AND increase from Baseline ≥ 60 ms
- QTcF interval > 480 ms associated with syncope, life-threatening arrhythmias, resuscitated cardiac arrest, or seizure

The Investigator must also discontinue/withdraw a patient's participation in the study if any of the following criteria apply:

- Pregnancy
- Significant protocol violation/lack of compliance with the study and/or study procedures non-compliance with IP for discontinuation of patient is defined as < 50%.
- Severe constipation (e.g., obstipation with manual evacuation indicated) and/or severe, persistent, or worsening abdominal pain
- Any significant worsening on postdose C-SSRS indicative of active suicidal ideation with intent to act (defined as C-SSRS Suicidal Ideation category score of 4 or 5) or behavior (either preparatory acts/behavior, aborted attempt, interrupted attempt, or actual attempt)
- Severe depression or anxiety based on a HADS Depression or Anxiety score ≥ 15, or a QIDS-C Total Score ≥ 16.

• Any severe psychiatric or CNS AE as determined by the Investigator.

The Investigator may discontinue/withdraw a study patient's participation in the study if any of the following criteria apply:

Protocol RVT-1201-2002

Effective: 19JAN2022

• Behavioral or administrative reason

Any clinical AE, laboratory abnormality, or other medical condition or situation occurs such that continued participation in the study would not be in the best interest of the patient. When applicable, patients should be informed of circumstances under which their participation may be terminated by the Investigator without their consent.

